6.3.1 Sensitivity analysis to account for dropouts

Sensitivity analyses will be performed if at least one confirmed recurrent event occurred within the 30 days intended treatment period in order to evaluate the potential influence of dropouts on the incidence of the primary efficacy outcome for the treatment period up to visit 4. In these analyses subjects with premature termination before visit (no follow-up until Day 30) will be assumed as having hazard of recurrence of VTE (primary efficacy outcome) 1.5 times (scenario 1) and twice (scenario 2) as high as the hazard calculated including all patients within each treatment group assuming informative censoring. For this sensitivity analysis exponential distribution for the event rates (hazard) will be assumed and the analysis will be performed for the rivaroxaban treatment group. This method is an application of methods for informative missingness odds ratio (IMOR) by White et al (5).

- $t_j \sim \exp(h_{\text{non-informative}})$
 $P_{\text{non-informative}} = 1 - e^{-(30 \cdot h_{\text{non-informative}})}$
 $h_{\text{dropout}} = h_{\text{non-informative}} \cdot \text{IMHR}$
 $P_{\text{overall}, j} = 1 - e^{-(t_j \cdot h_{\text{non-informative}} + [30 - t_j] \cdot h_{\text{dropout}})}$
 $P_{\text{overall, mean}} = \text{mean}(P_{\text{overall}, j})$

where

t_j : event times (or censoring) of patient j .

$h_{\text{non-informative}}$: hazard of the primary efficacy outcome assuming non-informative censoring using all patients' data.

$P_{\text{non-informative}}$: the cumulative event probability at Day 30 based on the exponential model.

h_{dropout} : hazard of the primary efficacy outcome after dropping out.

$P_{\text{overall}, j}$: cumulative event probability at Day 30 calculated based on mixture of $h_{\text{non-informative}}$ up to drop out and h_{dropout} from drop out up to Day 30 using exponential model for patient j .

$P_{\text{overall, mean}}$: mean of the cumulative event probability.

IMHR: informative missingness hazard ratio.

- Prior for log hazard (non-informative censoring):
 $\log(h_{\text{non-informative}}) \sim \text{dnorm}(-6.6, 1/\sqrt{0.4})$.
- Priors (informative) for IMHR:
IMHR $\sim \ln N(\mu, \sigma)$ where
 $\mu = \text{scenario 1: } \ln(1.5) = 0.405$; scenario 2: $\ln(2) = 0.693$ and
 $\sigma = 1/\sqrt{10} = 0.316$.

The analysis will be done with an Bayesian Markov Chain Monte Carlo (MCMC) simulation approach (e.g. with OpenBUGS Version 3.2.3 or other). For an example code see Appendix, Section 9.2.

6.4 Pharmacokinetics / pharmacodynamics

Individual profiles and summary statistics overall and by weight groups will be provided for PK/PD data. PK/PD modeling, using population approaches will be used to describe the pharmacokinetics of rivaroxaban, including potential influence of relevant co-variables, and relation of anticoagulant parameters of rivaroxaban with plasma concentrations. Details will be given in a separate PK/PD evaluation plan.

6.5 Safety

6.5.1 Study drug exposure and compliance

The descriptive statistics in this section will be done for all data combined and for each age cohort.

6.5.1.1 Summary of treatment duration

The overall treatment duration will be summarized descriptively in the safety analysis set and in the per protocol analysis set.

6.5.1.2 Summary of compliance

Counts and percentages will be tabulated for the following compliance categories in the safety analysis set:

Missing, Compliance <50%, Compliance $\geq 50\%$ to <80%, Compliance $\geq 80\%$.

The volume and type of fluid used to predilute the rivaroxaban oral suspension, as well as the volume and type of fluid taken after the study drug administration will be summarized by visit, overall and by age group.

6.5.1.3 Summary of INR measurements for the VKA treatment

This section is applicable only if a patient received VKA as study medication before Protocol Amendment 4. Proportion of patients with INR <2, within 2 to 3 INR inclusive and INR >3 will be summarized for the one month main treatment period using the observed INR values.

6.5.2 Adverse events

Individual listings of adverse events (including age, weight, height, gender, adverse event as reported, start, duration, severity and relation to study drug) will be provided. The incidence of treatment-emergent adverse events will be summarized by age group, using MedDRA preferred terms, grouped by primary system organ class. Time window for treatment-emergent events is defined as events occurring after start of study medication (for patients randomized to the standard of care group before Protocol Amendment 4 after IxRS assignment) until last intake of study medication plus 2 days. The incidences will be presented for all data combined and for each age cohort separately. Incidences of other vascular events and all deaths will be summarized, too.

For the purpose of adverse event (AE) documentation, study drug is defined as either rivaroxaban or standard of care as allocated starting from IxRS assignment up to the end of study treatment visit.

6.5.3 Laboratory measurements

Descriptive statistics will be presented for Hb, platelets, ALT, total and direct bilirubin at visit 4 (Day 30) and for their changes to baseline. The descriptive statistics will be done for all data combined and for each age cohort. Additional lab data at visit 3 (Day 15) and their changes to baseline will be summarized for patients from Canada separately. For the calculation of the mean value an anti-Xa activity value below LLOQ will be substituted by one half of this limit. In tables showing descriptive statistics, where values below LLOQ are included in the calculation of mean values, these means will be marked. All other lab values including aPTT and PT with the qualifier '< i.e less than' will be considered for descriptive statistics with their values without the qualifier. All lab values with the qualifier '> i.e. greater than' will be considered for descriptive statistics with their values without the qualifier.

6.6 Pre-specified subgroup analysis

6.6.1 Analysis by baseline characteristics

The baseline, efficacy, bleeding and safety analyses will be done by age cohort and by baseline presentation of venous thrombosis as described in sections [6.1](#), [6.2](#), [6.3](#), [6.5.1](#).

6.7 Taste and texture questionnaire

Results for the taste-and-texture questionnaire in children older than 4 years who receive the oral suspension will be presented descriptively as counts and proportions of responses by questions.

7. Document history and changes in the planned statistical analysis

First draft of SAP was circulated with the Bayer team on 10 Dec 2014.

Version 1.0: 26 Jun 2015.

SAP Version 2.0 dated 28 Apr 2017 was prepared to provide the following edits. None of them are considered to change the primary efficacy analysis and other analyses as described, but includes additional analyses and further clarifications:

- There is a typo in the date of Version 1.0: it was finalized on 26 Jun 2015 and not in 2014.
- No by visit compliance will be calculated, because drug accountability data were not to be recorded at visit 3. The calculations of compliance were further specified.
- The definition of the per protocol set was updated based on the decisions of the blind review meetings: This population includes all enrolled children who had at least 25 days study treatment. Children who discontinued study treatment earlier than 25 days due to an efficacy or bleeding outcome or due to a procedure defined in the study protocol or withdrew consent will not be excluded from the per protocol set. If a child died having less than 25 days study treatment, they will not be excluded from the per protocol set. Children with a calculated compliance less than 50% will be excluded from the per protocol set, calculated compliance between 50% and less than 80% and greater than 120% is considered as minor protocol deviation.
- Added PK analysis set and PD analysis set based on the decisions of the blind review meetings.
- Treatment groups will be displayed as study medication administered.
- Antithrombotics started after stop of study medication will be displayed only.
- Analysis of demographic, medical history and efficacy was further clarified, analysis of and PK/PD data by weight was included.
- Sensitivity analysis as described in Section 6.3.1 will be done only if at least one confirmed recurrent event occurred within the 30 days intended treatment period.

8. References

1. The EINSTEIN investigators. Oral Rivaroxaban for Symptomatic Venous Thromboembolism. *N Engl J Med* 2010; 363: 2499-2510.

9.1 Sample size and power considerations

A total of 20 children who took at least one dose of rivaroxaban study medication are planned to be enrolled in the study according to Global Amendment 4 to the Study Protocol. This sample size does not originate from a formal sample size calculation, but is based on a feasibility assessment. For observed incidences of safety and efficacy incidences see the results of the Einstein VTE treatment program in adults (1, 2, 3). Table 9-1 shows 95% exact confidence intervals (Blyth–Still–Casella interval; 6) for a range of potential incidence of safety and efficacy clinical outcomes (see Section 3.3 for outcomes in this study).

Table 9-1: 95% exact Blyth–Still–Casella confidence intervals around the estimated incidences for 20 patients.

Incidence	Blyth-Still-Casella confidence interval
0/20 (0%)	0.0% to 15.4%
1/20 (5%)	0.3% to 23.1%
2/20 (10%)	1.8% to 31.5%
3/20 (15%)	4.2% to 36.1%
4/20 (20%)	7.1% to 41.1%

This study with 20 children on rivaroxaban will allow for a description of the efficacy and safety outcomes as well as the PK and PD characteristics of rivaroxaban in the pediatric patient population.

9.2 Example OpenBUGS code for sensitivity analysis of the primary efficacy outcome

OpenBUGS model

```
Model { for (i in 1 : N) {
  # Survival times bounded below by censoring times, noninformative censoring
  t[i] ~ dexp(mu[i])C(t.cen[i],)
  mu[i] <- exp(alpha)
  im.alpha[i] <- alpha + log.IMHR
  lambda.1[i] <- -(t.obs[i] * exp(alpha) + (t.limit - t.obs[i]) * exp(im.alpha[i]))
  p.im1[i] <- 1 - exp(lambda.1[i]) }
  alpha ~ dnorm(-6.6, 0.4)
  exp.alpha <- exp(alpha)
  # IMHR = 2
  log.IMHR ~ dnorm(0.693, 10)

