6.1 Study visits - amended

The study has 5 planned visits (see [Figure 1–1](#)).

Visit 1 is a screening visit and will be a hospital visit. This visit is to identify potential eligibility of children who are treated with anticoagulants for confirmed symptomatic or asymptomatic venous thrombosis. This visit will take place 60 to 10 days before Visit 2.

Visit 2 is the first study drug administration day and will be a hospital visit. Eligible children will receive rivaroxaban for 30 days.

Visit 3 and Visit 4 are the treatment and end of treatment visits, respectively. These visits will be hospital visits which will take place at Day 15 ± 5 days, and Day 30 ± 3 days, respectively. At visit 2, 3 and 4, PK/PD blood samples will be drawn. At Visit 4, the study medication will be stopped. After cessation of study treatment, it is at the investigator's discretion to continue with anticoagulation, as needed. Repeat imaging will be obtained if applicable.

Visit 5 is the 30 day post treatment contact visit and will be a hospital visit or a telephone contact. It will take place at Day 60 ± 7 days. This visit will be the last study visit.

In children who prematurely discontinue study medication, visit 5 will take place 30 ± 7 days after premature discontinuation.³⁴

6.2 Visit 1 - Screening visit at 60 to 10 days before Visit 2 - amended

The parents/legal guardians will be given explanation about the study and will be given sufficient time to consider participation of their child in the study. Parents/legal guardians who are willing to have their child participating in the study will be asked to sign an informed consent form.

Screening will only be performed after having received informed consent. Children who pass the screen of inclusion and exclusion criteria can be enrolled into the study.

Then demographic data, medical history, height/length, blood pressure and anticoagulant medication will be collected.

The images of the index venous thrombotic event need to be collected and the adjudication package needs to be completed and sent to the central adjudication office. The CIAC will assess the images and will inform the investigator about their decision.

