6.3 Efficacy

All efficacy analyses will be performed on the full analysis set population based on the outcomes confirmed by the CIAC. Incidence proportions will be calculated for the efficacy outcomes (see Section 3.3) overall and by age stratum for the rivaroxaban group and for the standard of care group (randomized before Protocol Amendment 4) separately. The analyses described above will include events up to the end of intended study treatment (30 days after study medication assignment) regardless of the actual stop date of study medication.

In addition if there is at least one confirmed recurrent event in the corresponding time period, the analyses described above will be performed counting only events that occurred during study treatment or within 2 days after stop of study medication (i.e. treatment-emergent) on the safety population as well.

Proportion of events that occurred more than 2 days after stop of study medication up to 30 days will be described (denominator: number of subjects entering the observational period) if there is at least one confirmed recurrent event in the corresponding time period.

In addition, all descriptive efficacy analyses will be performed on the per protocol population as a supportive analysis.

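### The dropout sensitivity formula applies the raised hazard to every child's time short of Day 30, not only to dropouts, so a child with a recurrence, and possibly completers, are counted as lost

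*SAP*

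**What the plan says.** SAP 6.3.1 states who carries the raised hazard: "subjects with premature termination before visit (no follow-up until Day 30) will be assumed as having hazard of recurrence of VTE" 1.5 times (scenario 1) or twice (scenario 2) that of the whole group. It also states for how long: "from drop out up to Day 30 using exponential model for patient j".

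The formula in 6.3.1 and the code in 9.2 are broader. Child j's cumulative hazard is t_j at the base hazard plus (30 − t_j) at the dropout hazard, and the code loops this over all children: "lambda.1[i] <- -(t.obs[i] * exp(alpha) + (t.limit - t.obs[i]) * exp(im.alpha[i" (closing brackets omitted). Time t_j is defined only as "event times (or censoring) of patient j". Neither place caps t_j at 30 or marks who dropped out.

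The end of the period is described in two ways. SAP 6.3.1 assesses the "primary efficacy outcome for the treatment period up to visit 4", and Protocol 6.1 places Visits 3 and 4 at "Day 15 ± 5 days, and Day 30 ± 3 days, respectively". SAP 6.3 says the main efficacy analyses "include events up to the end of intended study treatment (30 days after study medication assignment) regardless of the actual stop date of study medication".

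The sensitivity analysis runs only if at least one confirmed recurrence falls within the intended 30 days.

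**The concern.** The analysis is meant to show how far dropouts could change the estimated recurrence risk. With no dropouts it should return the non-informative estimate unchanged. The formula does so only if every t_j equals exactly 30. Two groups of non-dropouts can break that:

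- **A child with a recurrence before Day 30.** Here t_j is the event time, so the days from the event to Day 30 are charged at the dropout hazard although the outcome is known. Since the analysis runs only when a recurrence has occurred, this affects every run in which that event came before Day 30.
- **Completers, if t_j is the Visit 4 day.** A visit on Days 27 to 29 adds dropout time. A visit on Days 31 to 33 makes (30 − t_j) negative and pulls the pessimistic scenario below the base case.

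At stake is whether a reported shift can be read as the influence of dropouts.

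**Working it through.** **Inputs.** From SAP 6.3.1 and 9.2: log h is normal with mean −6.6 and precision 0.4 (SD 1.58); log IMHR is normal with mean ln 1.5 or ln 2 and precision 10 (SD 0.316); event times are exponential. From SAP 9.1: 20 children. From Protocol 6.1: Visit 4 on Days 27 to 33. Assumed: `t.limit` = 30, from the 6.3.1 formula, and one recurrence.

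**Formulas.** With d events over T child-days, the posterior of log h is proportional to prior × h^d × exp(−hT).
- Non-informative estimate: mean of 1 − exp(−30h).
- Sensitivity estimate: mean over children of 1 − exp(−[t_j·h + (30 − t_j)·h·IMHR]).

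Both were integrated numerically over h and IMHR.

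**The SAP's example output.** It shows 0.07132 and 0.09599 (ratio 1.346), with alpha −6.298 (SD 0.8361). Its data are not printed, so it cannot be reproduced exactly. An assumed set of 20 children, one event and 370 child-days gives 0.0695 and 0.0961, with alpha −6.38 (SD 0.94). That is near but not identical; the SAP run used 1,000 draws with a Monte Carlo error of 0.056 on alpha.

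**Step 1: the child with the event.** One event at Day 15, 19 children at Day 30, no dropouts, IMHR fixed at 2:
- Event child: 15h + 15 × 2h = 45h instead of 30h.
- Average: (45 + 19 × 30)/20 = 30.75h, which is +2.5%.
- With the SAP priors: 5.08% becomes 5.21%, which is +2.6%.
- An earlier event shifts it more: Day 10 gives a ratio of 1.034 and Day 5 gives 1.042.

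**Step 2: completers, if t_j is the Visit 4 day.** At fixed IMHR 2, Day 27 gives 27h + 3 × 2h = 33h and Day 33 gives 33h − 3 × 2h = 27h. At IMHR 1.5 these are 31.5h and 28.5h. With the SAP priors, one event, no dropouts and all 20 times on the same day:

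| Day | Non-informative | Scenario 2 (ratio) | Scenario 1 ratio |
|---|---|---|---|
| 27 | 5.37% | 5.93% (1.104) | 1.055 |
| 30 | 4.99% | 4.99% (1.000) | 1.000 |
| 33 | 4.66% | 4.16% (0.894) | 0.944 |

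**Step 3: realistic scatter.** If visits spread evenly over Days 27 to 33, the mean of (30 − t_j) is zero and so is the average shift. For 20 random days the SD of one day is 2, so the mean has SD 2/√20 = 0.45 days. In scenario 2 that gives 1.96 × 0.45/30 = 2.9%. Simulation gives 95% of shifts within ±2.8% (scenario 2) and ±1.4% (scenario 1).

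**Step 4: with real dropouts.** Three dropouts at Day 10, one event at Day 15 and 16 children at Day 30, scenario 2: the formula as written moves 5.48% to 6.16% (+12.6%). Restricting the multiplier to the three dropouts gives 6.02% (+10.0%). The difference comes from the child with the event.

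The sign can also reverse. One dropout at Day 10, one event at Day 15 and 18 completers entered at Day 33 gives 4.88% to 4.70%.

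**The case against.** The strongest reply is that the completer error rests on an input the SAP does not fix. The code takes `t.obs` as supplied data. SAP 6.3 counts events to 30 days after assignment, and 6.3.1 defines its probabilities at Day 30. Visit 5, at Day 60 ± 7 (Protocol 6.1), gives outcome follow-up past Day 30 for a child seen on Day 27. A programmer who censors every followed child at Day 30 gives completers no dropout time. This stands: the completer part is an ambiguity created by the words about Visit 4, not a certain error.

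It does not clear the child with the event. That child's t_j is the event time by the SAP's own definition, so Step 1 remains after censoring at Day 30.

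A reader might infer that the result will move by about 10% with no dropouts, or that ordinary visit scatter matters as much as several real dropouts. The documents do not support that. The 10% needs all 20 children at the same edge of the window, scenario 2, and t_j set to the visit day. A 10% shift equals about four of 20 children dropping out at Day 15 at IMHR 2 ((4 × 45 + 16 × 30)/20 = 33h), whereas random scatter gives roughly ±3%.

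It is also fair that the code is labelled an example and that no conclusion would turn on this. The largest shift in the table is 5.93 − 5.37 = 0.56 percentage points, against the SAP's own interval of 0.3% to 23.1% for 1 in 20.

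**Conclusion.** The formula and code do not implement the dropout definition in the same section. This is a wrong rule, not only missing detail, because it charges dropout time to a child whose event is already known.

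- **Child with the event:** +2.6% relative (0.13 percentage points) in scenario 2 for one event at Day 15. This assumes 20 children, no dropouts and the SAP priors.
- **Completers:** conditional on t_j being the Visit 4 day. The bound is about ±10% in scenario 2 and ±5% in scenario 1. The average is about zero under even scatter, and the effect vanishes if followed children are censored at Day 30.

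Severity is minor. The analysis is conditional on a recurrence, concerns a secondary outcome, and sits in a descriptive single-arm study.

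**What to change.** In SAP 6.3.1 and 9.2:

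1. Set t_j = min(event time or last outcome follow-up, 30). Count Visit 5 as follow-up, so that every event-free child followed past Day 30 has t_j = 30. Use the same times in the likelihood.
2. Use cumulative hazard = t_j·h + (30 − t_j)·h·IMHR^D_j, with D_j = 1 only for children without an event and without follow-up to Day 30, and D_j = 0 otherwise. In the code, multiply `log.IMHR` by D_j in the line that defines `im.alpha`.

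Every non-dropout then contributes 30h, and with no dropouts the result equals the non-informative estimate (ratio 1.000).

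Two simpler repairs fall short:
- **A cap alone** corrects Days 31 to 33 but leaves Day 27 at 1.104 in scenario 2, and does nothing for the child with the event.
- **Multiplying (30 − t_j) by a zero indicator** while t_j stays at the visit day deletes those days from the risk. With all children at Day 27 it gives 4.85% against 5.37%, about −10%. The indicator must remove the multiplier, not the time.

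The cost is one line of SAP text, one indicator variable and one changed line of code. No new data are needed.

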  # Results from informative censoring
  CDF.1 <- 1 - exp(-(t.limit * exp.alpha))
  p.mean.im1 <- sum(p.im1[])/N1 }
```

Openbugs node statistics

	mean	sd	MC_error	val2.5pc	median	val97.5pc	start	sample
CDF.1	0.07132	0.0552	0.003239	0.008807	0.05557	0.2108	1001	1000
alpha	-6.298	0.8361	0.05607	-8.129	-6.263	-4.842	1001	1000
p.mean.im1	0.09599	0.07443	0.004247	0.01128	0.07357	0.281	1001	1000

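### The dropout sensitivity model's unsourced hazard prior (median 30-day risk 4.0%) lowers the modelled recurrence risk by about 1 to 3 points with two or more events, so a pessimistic scenario with few dropouts can print below the crude rate

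*SAP*

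**What the plan says.** SAP 6.3.1 makes the analysis conditional: "Sensitivity analyses will be performed if at least one confirmed recurrent event occurred within the 30 days intended treatment period". Children lost before Day 30 are given a recurrence hazard 1.5 times (scenario 1) or twice (scenario 2) the "hazard calculated including all patients within each treatment group". The model is parametric: "exponential distribution for the event rates (hazard) will be assumed".

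Under the item "Prior for log hazard (non-informative censoring", 6.3.1 gives a normal prior with mean -6.6 and second argument 1/sqrt(0.4). The code in 9.2 has "alpha ~ dnorm(-6.6, 0.4", where OpenBUGS reads 0.4 as a precision. Neither section says where -6.6 comes from, and no alternative prior is planned.

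Two results are produced. One is "the cumulative event probability at Day 30 based on the exponential model", coded as "CDF.1 <- 1 - exp(-(t.limit * exp.alpha". The other is the scenario estimate, the mean of the children's modelled risks, coded as "p.mean.im1 <- sum(p.im1[])/N1". The main efficacy result in SAP 6.3 is the crude incidence proportion on the full analysis set. SAP 9.1 plans 20 children on rivaroxaban.

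**The concern.** The analysis is meant to show how much worse recurrence might be if the lost children fared worse than those followed. It starts from a base hazard that is pulled towards a prior centre of 4.0% over 30 days, while the smallest result that can trigger it in 20 children is 5%. With a handful of events the prior carries weight. The information in the data about the log hazard is roughly the number of events, so a prior precision of 0.4 takes about 0.4/2.4 = 17% of the weight with two events and 0.4/4.4 = 9% with four.

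The downward pull and the upward dropout multiplier therefore work against each other. If few children are lost, the pull can win, and a scenario labelled pessimistic then appears in the report below the crude proportion it is meant to stress.

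**Working it through.** **Inputs from the SAP.** Prior mean -6.6 and precision 0.4 (9.2; SD 1/sqrt(0.4) = 1.58). Horizon 30 days. Multiplier prior: log-normal, centred on 1.5 or 2, precision 10 on the log scale. N = 20. Trigger: at least one event.

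**Assumptions, not in the SAP.** Events at Day 15, dropouts at Day 10 (Day 15 as a variation), posterior means reported.

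**The SAP's own figures.** Putting the printed quantiles of alpha (-8.129, -6.263, -4.842) into 1 - exp(-30 x exp(alpha)) gives 0.00881, 0.05556 and 0.2108. The printed `CDF.1` quantiles are 0.008807, 0.05557 and 0.2108. The scale and horizon are confirmed. The data behind that example are not listed, so its posterior cannot be fully rebuilt.

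**Prior.** exp(-6.6) = 0.00136 per day, and 1 - exp(-30 x 0.00136) = 4.0%. The 95% range is about 0.2% to 60%, the mean 9.9%, and 44% of the prior mass lies above 5%. The triggering floor 1/N stays above 4.0% up to N = 24 (1/24 = 4.17%).

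**Base risk, no dropouts.** With d events, person-days T = 600 - 15d. Maximum likelihood: 1 - exp(-30d/T). Flat log-hazard prior: the hazard is Gamma(d, T), so the mean risk is 1 - (T/(T+30))^d; for d = 2 this is 1 - (570/600)^2 = 9.75%. SAP prior: posterior proportional to exp(d x alpha - T x exp(alpha) - 0.2 x (alpha + 6.6)^2), integrated on a grid.

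| Events | Crude % | T | Max. likelihood % | Flat prior % | SAP prior % |
|---|---|---|---|---|---|
| 1 | 5 | 585 | 5.0 | 4.88 | 5.1 |
| 2 | 10 | 570 | 10.0 | 9.75 | 8.7 |
| 3 | 15 | 555 | 15.0 | 14.61 | 12.7 |
| 4 | 20 | 540 | 19.9 | 19.45 | 17.0 |

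Against the crude rate the shortfall for 2, 3 and 4 events is 1.3, 2.3 and 3.0 points. Against the flat-prior mean it is about 1.1, 1.9 and 2.5 points, which is the part due to the prior.

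**Scenario estimate as coded.** For each child, risk = 1 - exp(-[t x h + (30 - t) x h x IMHR]), averaged over 20. As in both 6.3.1 and 9.2, t is the event or censoring time, so the (30 - t) term also applies to children with an event.

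| Case, dropouts at Day 10 | 2/20 (10%) | 3/20 (15%) | 4/20 (20%) |
|---|---|---|---|
| Scenario 1, 1 lost | 9.3 | 13.8 | 18.6 |
| Scenario 1, 2 lost | 9.7 | 14.4 | 19.5 |
| Scenario 2, 1 lost | 9.7 | 14.4 | 19.6 |
| Scenario 2, 2 lost | 10.2 | 15.3 | 20.7 |
| Scenario 2, 3 lost | 10.8 | 16.2 | 21.9 |
| Scenario 2, 1 lost, near-flat prior | 10.9 | 16.6 | 22.4 |

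With dropouts at Day 15, scenario 2 gives 9.5, 14.3 and 19.3% for one lost, and 9.9, 14.9 and 20.1% for two, which is about the crude rate.

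**The case against.** A weakly informative prior is a defensible choice with one to four events, and this one is wide. The gap is small: for 2/20 with one child lost, scenario 2 gives 9.7% with a 95% credible interval of about 1.6% to 24.8%. The study is descriptive and single-arm, and no threshold hangs on the figure. All of this stands and limits the size of the point.

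Four stronger readings are tempting, and the documents do not support them:

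- **The pessimistic scenario always falls below the crude rate when one or two children are lost.** In scenario 2 with two lost, that holds only if the raised hazard is applied to lost children alone (9.8, 14.3 and 19.1%). The SAP formula as written gives 10.2, 15.3 and 20.7%.
- **The output would suggest that dropouts do not matter.** The SAP prints `CDF.1` beside `p.mean.im1`, and in its example the mean rises from 7.1% to 9.6%. Within the model the dropout effect is visible and in the right direction. The shortfall is against the crude proportion in 6.3.
- **6.3.1 contradicts itself by calculating the hazard from all patients and then using a prior.** The first statement says whose data enter, and the prior is stated openly in the same section.
- **The text and the code specify different priors.** 1/sqrt(0.4) fits the SD convention that 6.3.1 uses for the multiplier (sigma = 1/sqrt(10), precision 10 in the code). Only a programmer who typed the text form into OpenBUGS would get SD 0.80, and then 3/20 with no dropouts would give 9.3%. The 9.2 code guards against this.

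Nor is the whole shortfall due to the prior. Even a flat prior gives posterior means slightly below the crude rates when nobody is lost (9.75, 14.61 and 19.45%).

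**Conclusion.** The point holds as a modest downward bias in a conditional, supportive analysis. With two or more events and few dropouts, the unsourced prior lowers the modelled base risk by about 1 to 3 points. As coded, scenario 1 with one or two lost at Day 10, and scenario 2 with one lost, both print below the crude proportion. Scenario 2 with two or more lost at Day 10 is above it.

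With a single event the posterior mean is not lowered (5.1% against 5.0%). The posterior median is about 4.0%, but part of any shortfall in medians is skewness.

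The figures rest on N = 20, the assumed event and dropout days, and posterior means; the SAP does not say which summary it will report. If the full analysis set exceeds 24, the prior median is no longer below the smallest triggering result. No formal decision depends on the outcome. The case for changing it is that a stress test should not start from an unexplained favourable shift.

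**What to change.** In SAP 6.3.1 and 9.2, use a near-flat prior on the log hazard, for example `alpha ~ dnorm(0, 0.001)` in precision form, or add it as the reference run beside the present prior. Because at least one event is required, the posterior is essentially Gamma(events, person-days) and well behaved. If -6.6 is kept, state its source.

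Write the prior in one parameterisation in both sections. Report each scenario next to `CDF.1` and the observed proportion, and name the posterior summary used.

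The cost is one code line and some wording. Credible intervals become slightly wider (upper limit about 17.2% instead of 15.8% for 1/20), and the figure is slightly less favourable with two or more events.
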